7.10 Unscheduled Angiography/Intervention

For all unscheduled angiographies and revascularizations, the angiogram must be sent to the CRO, regardless of whether target or non-target vessel revascularization was performed. The Clinical Event Committee (CEC) will adjudicate the type of revascularization indicating if the revascularization is clinically indicated or not clinically indicated, etc. (See Appendix I:

Definitions). Routine follow-up angiography (in the asymptomatic patient) is not permitted in this study and the reasons for follow-up angiography will be closely tracked in the case report form.

In patients who do undergo follow-up angiography, repeat PCI or CABG may only be performed with evidence of ischemia, requiring one of the following to be present:

- $\geq 70\%$ diameter stenosis of the treated or new lesions by visual angiographic assessment
- In the case of a visually estimated diameter stenosis of $\geq 50\%$ to $< 70\%$, either
 - evidence of definite ischemia in the territory of the diseased vessel by prior non-invasive stress* testing with imaging evaluation showing ischemia in the questioned myocardial territory, and/or
 - IVUS minimal stent area $\leq 6.0 \text{ mm}^2$ for left main lesions or $\leq 4.0 \text{ mm}^2$ for non left main lesions, and/or
 - intra-procedure FFR ≤ 0.80 /iFR ≤ 0.89 .

*stress test is not advised within 8 weeks after stent implantation.

IVUS is preferred for assessment of left main lesions, and iFR is preferred for assessment of non-left main lesions. In particular, after left main stent implantation, the ostial LCX may often appear significantly or even severely stenosed in the absence of symptoms or ischemia (“pseudostenosis”). All patients with a suspected ostial LCX stenosis, regardless of the degree of angiographic severity (unless occluded), are highly recommended to have demonstrated an iFR ≤ 0.89 (or FFR ≤ 0.80 when available) in the LCX prior to repeat revascularization, unless there is unequivocal evidence of lateral wall ischemia on non-invasive stress testing.

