- *When biomarker levels are stable or falling*, there should be new CK-MB elevation by an absolute increment of $\geq 10 \times \text{ULN}$ (or $\geq 70 \times \text{ULN}$ for cTnI or T) from the previous nadir level
- *When biomarker levels have not been shown to be stable or falling*, there should be a further rise in CK-MB or troponin beyond the most recently measured value by an absolute increment of $\geq 10 \times \text{ULN}$ in CK-MB or $\geq 70 \times \text{ULN}$ in cTn plus new ST-segment elevation or depression plus signs consistent with a clinically relevant MI, such as new onset or worsening heart failure or sustained hypotension.

While not currently recommended as part of this definition, use of post-CABG ECGs, indices of hemodynamic instability, and imaging studies demonstrating new wall motion abnormalities are suggested to complement biomarker elevations post- CABG to improve specificity.

REVASCULARISATION

[Target Lesion]

A lesion revascularized in the index procedure (or staged procedure). The left-main target lesion extends from the distal left main stem to the end of the 5 mm proximal segments of the left anterior descending and left circumflex arteries as well as the ramus intermedius if the latter vessel has a vessel diameter of ≥ 2 mm.

[Target Vessel]

The target vessel is defined as the entire major coronary vessel proximal and distal to the target lesion including upstream and downstream branches and the target lesion itself. The left main

and any vessel originating from the left main coronary artery or its major branches is, by definition, considered a target vessel for the purposes of this trial (unless either the LAD or LCX are occluded at baseline and no attempt was made to revascularize these territories by PCI).

[Target Vessel-Non-Target Lesion]

The target vessel but non-target lesion consists of a lesion in the epicardial vessel/branch that contains the target lesion; however, this lesion is outside of the target lesion by at least 5 mm distal or proximal to the target lesion determined by coronary angiography.

[Non-Target Vessel]

For the purposes of this trial, the only possible non-target vessel would be the right coronary artery and its major branches that were not treated by PCI at the index procedure (unless either the LAD or LCX are occluded at baseline and no attempt was made to revascularize these territories by either PCI or CABG).

[Target Vessel Revascularization (TVR)]

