Target vessel revascularization is any repeat percutaneous intervention of the target vessel or bypass surgery of the target vessel.

[Target Lesion Revascularization (TLR)]

Target lesion revascularization is defined as any repeat percutaneous intervention of the target lesion or bypass surgery of the target vessel.

[Clinically-Indicated Revascularization (CI-TLR/TVR)]

Revascularization will be considered ischemia-driven if the target lesion diameter stenosis is $\geq 50\%$ by QCA and any of the following criteria for ischemia are met:

- Positive functional ischemia study including positive FFR/iFR corresponding to the area served by the target lesion; or
- Ischemic ECG changes at rest in a distribution consistent with the target vessel; or
- Typical ischemic symptoms referable to the target lesion; or
- IVUS of the target lesion with a minimal lumen area (MLA) of $\leq 4\text{mm}^2$ for non left main lesions or $\leq 6\text{mm}^2$ for left main lesions. If the lesions are de novo (i.e. not restenotic), the plaque burden must also be $\geq 60\%$; or
- FFR of the target lesion ≤ 0.80 or iFR of the target lesion ≤ 0.89 .

A target lesion revascularization for a diameter stenosis less than 50% might also be considered ischemia-driven by the Clinical Events Committee if there was a markedly positive functional study or ECG changes corresponding to the area served by the target lesion.

STENT THROMBOSIS

(ARC)⁴²

Stent thrombosis should be reported as a cumulative value at the different time points and with the different separate time points. Time 0 is defined as the time point after the guiding catheter has been removed and the patient left the catheterization lab.

Timing:

- Acute stent thrombosis*: 0 - 24 hours post stent implantation
- Subacute stent thrombosis*: >24 hours - 30 days post stent implantation
- Late stent thrombosis†: 30 days - 1 year post stent implantation
- Very late stent/ thrombosis†: >1 year post stent implantation

* Acute/subacute can also be replaced by early stent thrombosis. Early stent thrombosis (0 - 30 days) - this definition is currently used in the community.

† Including “primary” as well as “secondary” late stent thrombosis; “secondary” late stent thrombosis is a stent thrombosis after a target segment revascularization.

Categories:

- Definite
- Probable
- Possible

Definitions of each category are as follows.

- **Definite stent thrombosis**

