Iterative IVUS and post-dilation should be performed until the distal ULMCA minimum stent area is >8.5mm² and the ostial/proximal LAD minimum stent area is at least >6.0mm² and preferably matched to the distal reference vessel diameter if larger. Observational data in non-LMCA lesions has shown that in general the larger the minimal stent area the lower the likelihood of restenosis and stent thrombosis^{18, 51-53} and thus post-dilation with non compliant balloons sized up to 0.25-0.50 mm less than the IVUS determined true vessel diameter (average media-media dimension) to safely achieve the largest maximal luminal dimension is recommended. It is strongly recommended that IVUS is also performed post-stenting from at least one epicardial coronary artery, usually the LAD, with pullback into the aorta (disengaging the guide to ensure the ostium is not missed). If a 1-stent technique is used (most commonly from the ULMCA into the LAD, “crossing over” the LCX), it is desirable but not mandatory that the ostial LCX also be imaged post-intervention if possible. If a 2-stent technique is used, IVUS pullback across the LAD and LCX is strongly recommended if the IVUS catheter passes easily into the LCX. *LCX or side branch imaging should not be pursued aggressively to avoid IVUS related (or pressure wire-related) complications.* If the IVUS catheter or pressure wire can be safely positioned into the LCX, then, in general, an LCX ostium lumen area >4.0mm² (single stent strategy) or >5.5mm² (two stent strategy) or an FFR >0.80 (single stent strategy) indicates that no further intervention is necessary.^{18, 51-53}

Severe dissections present by IVUS (residual true lumen within the dissection flap below the above-mentioned criteria in each segment [LM: 8.5 mm², LAD: 6.0 mm², LCX: 5.5 mm²]) should in general receive an additional stent. Malapposition with stent area below the above-mentioned cut-off criteria in respective segment should in general be treated by additional post-dilatation with larger balloons.

IVUS and iFR for Guidance of other lesion (non-distal ULMCA PCI)

Pre-intervention non-distal ULMCA lesion assessment

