If IVUS is used to guide treatment of ULMCA lesions, it is recommended that IVUS also be used to guide treatment of important non-LMCA lesions in the LAD, LCX, and RCA circulations. XIENCE stent size and length should be selected and optimized to achieve a minimum stent area >5.5 mm² in non ULMCA lesions (with post-dilation with non compliant balloons sized up to 0.25-0.5mm less than the IVUS determined true vessel diameter (average media-to-media dimension), and to end the stents in arterial segments with a plaque burden <50%. Severe dissections present by IVUS (residual true lumen within the dissection flap ≤ 5.5 mm² either proximal or distal to the stent) should in general receive an additional stent. Malapposition with stent area ≤ 5.5 mm² should in general be treated by additional post-dilatation with larger balloons.

Follow-up

Since the site of restenosis after distal ULMCA bifurcation intervention is typically the ostium of the LCX, and since many presumed ostial LCX restenoses are angiographic artifacts (i.e. appear angiographically severe, but in fact are not hemodynamically significant),⁵⁶ it is strongly recommended that FFR/iFR be performed before treating any presumed restenotic lesions in the ostial LCX location (regardless of angiographic severity, unless totally occluded) unless there is unequivocal lateral wall ischemia by nuclear or echocardiographic noninvasive testing. If the FFR is >0.80 or iFR > 0.89 , the ostial LCX lesion should not be treated and, thus, TLR (and possible procedural complications) avoided. For sites that do not use FFR/iFR, it is strongly recommended that pre-interventional IVUS of the ostial LCX be performed instead with an MLA $>4.0\text{mm}^2$ used as the criteria to defer intervention and avoid TLR⁵⁷. Similarly, prior to performing a repeat intervention elsewhere in the coronary tree, if the visually assessed angiographic diameter stenosis is $<70\%$, ischemia should be documented according to either a positive nuclear or echocardiographic noninvasive test in the distribution of the recurrent lesion, or an FFR ≤ 0.80 /iFR ≤ 0.89 , or IVUS with a MLA $\leq 4.0\text{ mm}^2$.

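### Section 7.10's IVUS criterion for repeat revascularization names stent area where lumen area is meant, so restenosis inside a left-main-stem or confluence stent at the recommended size cannot meet it

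*Combined protocol and SAP*

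**What the plan says.** Section 7.10 is a binding rule on when repeat PCI or CABG may follow an unscheduled angiogram. A visual stenosis of 70% or more, in a treated or a new lesion, is enough alone. From 50% to below 70% at least one further item is needed:

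- ischemia on prior stress imaging;
- IVUS, worded as "IVUS minimal stent area" of at most 6.0 mm² for left main lesions or 4.0 mm² for other lesions;
- FFR of at most 0.80 or iFR of at most 0.89.

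The section prefers IVUS for left main lesions and iFR for others. For a suspected ostial LCX stenosis it directs the operator to iFR or FFR.

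Two other places set an IVUS criterion for the same kind of decision:

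- Appendix I, under clinically-indicated revascularization, has "IVUS of the target lesion with a minimal lumen area (MLA) of" at most 4 mm² (non left main) or 6 mm² (left main).
- Appendix II, under Follow-up, gives a rule that applies "prior to performing a repeat intervention elsewhere in the coronary tree". Its IVUS option reads "or IVUS with a MLA" of at most 4.0 mm².

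The stent-area targets at implantation are in section 7.4.3 (at least 8 mm² in the proximal left main, 7 at the confluence, 6 at the ostial LAD, 5 at the ostial LCX) and in Appendix II ("the distal ULMCA minimum stent area is >8.5mm²", and "to achieve a minimum stent area >5.5 mm² in non ULMCA lesions").

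**The concern.** Stent area and lumen area are different measurements from the same pullback. Stent area shows how well the stent was expanded. Lumen area shows how much channel is left. When tissue grows inside a stent the second falls and the first does not, so a stent-area criterion detects under-expansion and misses restenosis.

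The matching cut-offs suggest that a word was exchanged. The error still sits in a rule that operators must apply, and in the setting where the protocol prefers IVUS. Section 7.9 says that patients with cardiac symptoms or progressive disease should not have stress testing, above all when left main recurrence is possible. For stem or confluence restenosis of 50% to below 70%, that leaves FFR/iFR as the only item that can detect restenosis and is not discouraged.

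**Working it through.** The plan has no figure of its own to reproduce here. The check compares the cut-offs with the protocol's implant targets and then works out the lumen left inside a restenosed stent.

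**Inputs.** Cut-offs of 6.0 and 4.0 mm² (section 7.10, Appendix I). Stent targets of 8 and 7 mm² (section 7.4.3), above 8.5 and above 5.5 mm² (Appendix II). Left main diameter 3.0 to 4.5 mm (section 6.1, inclusion criterion 4). Assumptions: circular cross-sections, an accurate stenosis estimate, and stent area unchanged after implantation. The last is a property assumed of metallic stents and is not stated in the documents.

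**Step 1: stent at target size.** With the stent as reference, lumen area = stent area × (1 − stenosis)². The in-stent stenosis at which the lumen reaches the cut-off is 1 − √(cut-off / stent area).

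| Segment | Stent target (mm²) | Cut-off (mm²) | Stent wording met? | Lumen at 50% (mm²) | Lumen at 69% (mm²) | Lumen wording met? | Stenosis at which lumen reaches cut-off |
|---|---|---|---|---|---|---|---|
| Proximal left main | 8 | 6.0 | No | 2.00 | 0.77 | Yes | 13.4% |
| Confluence | 7 | 6.0 | No | 1.75 | 0.67 | Yes | 7.4% |
| Distal left main (Appendix II) | 8.5 | 6.0 | No | 2.125 | 0.82 | Yes | 16.0% |
| Non left main | 5.5 | 4.0 | No | 1.375 | 0.53 | Yes | 14.7% |

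The stent column does not depend on the degree of restenosis, so tighter disease never changes the answer.

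**Step 2: permitted left main diameters.** Area = π/4 × d².

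- A stent expanded to the reference diameter has 7.07 mm² at 3.0 mm and 15.90 mm² at 4.5 mm. Both exceed 6.0.
- A 50% stenosis halves the diameter and leaves 1.77 mm² and 3.98 mm². Both are below 6.0.
- The stent wording is met only if the stent is under-expanded to 6.0 / 7.07 = 85% of reference area at 3.0 mm, or 6.0 / 15.90 = 38% at 4.5 mm.

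Across the 50% to below 70% band the two wordings therefore give opposite answers for the left main stem, unless the stent is that far under-expanded.

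**Step 3: new lesions.** A lesion without a stent has no stent area. The item cannot be applied to it, although section 7.10 covers new lesions as well as treated ones.

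**Step 4: where the claim stops.** It does not extend to the ostia. If they count as left main, stents at their targets of 6 and 5 mm² are already at or below 6.0. Section 7.10 also sends the ostial LCX to iFR/FFR, and prefers iFR outside the left main, so the practical effect is limited to the stem and confluence.

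**The case against.** The strongest reply is that the consequence is small. The item is one of several alternatives and matters only from 50% to below 70%. At 70% or more no IVUS is needed. FFR/iFR stays open, and iFR is mandatory before the index procedure, so enrolling sites should have it. IVUS is preferred, not required. The stent targets are recommendations, and an under-expanded stent can meet the item. A sensible operator may also read stent as lumen. All of this stands and limits the size of the point. It does not make the item correct: the preferred left main test, read as written, cannot register restenosis in a stent of recommended size.

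A second reply is that Appendix I is a definition for classifying events and does not tell operators when to treat. That is fair, but the identical cut-offs still show which measurement they belong to.

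A reader might go further and infer that the left main stem has three conflicting IVUS rules: stent area 6.0, lumen area 6.0 and lumen area 4.0 mm². The documents do not support this. The Appendix II sentence follows text on ostial LCX restenosis and on lesions outside the left main, and it reaches the stem only on the most literal reading. The two lumen rules also agree here: a 50% stenosis leaves 1.77 to 3.98 mm² over the permitted left main range, which meets both.

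**Conclusion.** The item is wrong as written, and the error is in operative text. Section 7.10 names stent area for cut-offs that belong to lumen area. The conclusion rests on stent area staying as implanted, and step 2 also on circular geometry and an accurate stenosis estimate. The practical effect is limited to left-main-stem or confluence restenosis of 50% to below 70%. The documents give no count of such patients.

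Because unplanned revascularization for ischemia is part of PoCE, a reader might infer that patients are denied treatment or that the primary endpoint is undercounted. The documents do not show either. A stenosis of 70% or more, FFR/iFR and (though discouraged) stress imaging all remain as routes, so no patient is shown to be barred and no effect on PoCE is claimed.

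A reader might also think that the LAD and LCX ostia need their own cut-off, since "The left-main target lesion extends from the distal left main stem to the end of the 5 mm proximal segments" of those vessels. They do not. The item applies only once stenosis is already 50%. At that point a 6 mm² ostial LAD stent has a lumen of 6 × 0.25 = 1.5 mm², and a 3.75 mm main branch has π/4 × 1.875² = 2.76 mm². Both meet 4.0 and 6.0 alike.

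**What to change.** In section 7.10, replace the words minimal stent area with minimal lumen area (MLA). Keep the 6.0 and 4.0 mm² cut-offs, and keep the existing iFR/FFR direction for the ostial LCX. Notify sites.

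Nothing else has to change. Appendix II can stay as it is, and a separate ostial rule in section 7.10 would contradict Appendix I. The condition in Appendix I that begins "If the lesions are de novo (i.e. not restenotic), the plaque burden must also be" need not be copied into section 7.10: it would narrow a treatment permission and is not needed to correct the slip.

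The cost is one term in a protocol amendment and a short site memo. There is no new procedure, because lumen area and stent area come from the same IVUS pullback.

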7.11 Discontinuation of Follow-Up

At any time during the study, the patient may withdraw their participation from the study. Follow-up is only discontinued at the explicit request of the patient. This decision should be an independent decision that is documented in the patient study files. Survival status should be collected within legal and ethical boundaries for all patients enrolled who withdrew participation from the study. Data generated of any patient withdrawn from the trial will be included in the analysis unless the patient explicitly forbids the use of any data which should be documented by the site.

All patients are encouraged to return for all scheduled follow-up visits, and to provide appropriate contact information to accommodate completion of required telephone follow-ups. The investigator will attempt to contact the patient at each follow-up visit, independent of any

missed follow-ups. The investigator should make 3 documented attempts per required follow-up visit.

Patients who have discontinued the trial prematurely will not be replaced.

7.12 Patients Lost to Follow-Up

A patient would be considered lost to follow-up if he or she repeatedly fails to return for scheduled visits and is unable to be contacted by the study site. Only after failing to contact the patient at the final follow-up visit, the patient is considered lost to follow-up after last contact. Site personnel are expected to make diligent and documented attempts to contact patients who fail to return for a scheduled visit. It must be a high priority to obtain at least survival data on all patients lost to follow-up. Survival status will be collected within legal and ethical boundaries for all patients enrolled. Vital status will be searched in public sources at the end of the 1 year follow-up period. If vital status is known at the last study visit, the patient will not be considered lost to follow-up, notification of death by civil registry will be accepted.

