8.6 Missing data

Every effort will be undertaken to minimize missing data. Kaplan-Meier estimates will censor incomplete data at the date of last available follow-up information, assuming complete reporting of all events up to that date and event status unknown after that date.

Other missing information will be assumed Missing Completely at Random (MCAR). No imputation will take place for these data, nor is any sensitivity analysis planned.

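### Could a patient known only to be alive at one year be counted as free of stroke, MI and revascularization in the primary analysis?

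*Combined protocol and SAP*

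**What the plan says.** Section 8.1 estimates PoCE at 12 months by Kaplan-Meier and compares a one-sided 95% upper limit with the EXCEL rate plus the margin. By section 8.2 that target is 16.7% + 6.3% = 23.0%. Section 5.1 defines PoCE as death from any cause, stroke, any MI or unplanned revascularization for ischemia.

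On incomplete follow-up, section 8.6 states: "Kaplan-Meier estimates will censor incomplete data at the date of last available follow-up information, assuming complete reporting of all events up to that date", with "event status unknown after that date".

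Section 7.12 deals with conduct. After a failed final contact, "the patient is considered lost to follow-up after last contact". It then adds "Vital status will be searched in public sources at the end of the 1 year follow-up period", that "If vital status is known at the last study visit, the patient will not be considered lost to follow-up", and that "notification of death by civil registry will be accepted". Section 7.11 extends vital-status collection to withdrawals: "Survival status should be collected within legal and ethical boundaries for all patients enrolled who withdrew participation from the study". It also sets the effort required of sites: "The investigator should make 3 documented attempts per required follow-up visit".

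**The concern.** Section 8.6 does not name the kind of information that sets the censoring date. A public-source result showing the patient alive at day 365 is, in ordinary language, follow-up information, and 7.12 says such a patient is not lost. Put together, the two sections could let an analyst carry that patient to day 365 as event-free on every component. Vital status says nothing about stroke, MI or revascularization.

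The error would run one way. Unseen non-fatal events would become non-events, PoCE would fall, and the upper limit would move below 23.0% more easily. With a fixed target there is no control arm in which the same under-ascertainment could cancel. The protocol describes no sensitivity analysis for censored PoCE data; the sentence in 8.6 that rules one out concerns other missing information. Sections 7.12 and 8.6 also do not spell out how a death found only in a registry enters PoCE.

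**Working it through.** **Reading the sections together**

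- The trigger for censoring in 8.6 is incomplete data. It does not use the lost-to-follow-up label, so losing that label under 7.12 does not make a patient's data complete.
- 8.6 describes its date by two properties: all events before it are taken as reported, and event status after it is unknown. A visit, a phone call or a record review can meet the first property for PoCE. A look-up showing only that the patient is alive cannot.
- 7.12 places loss after the last contact, which points the same way.
- A registry death is already covered. Death from any cause is a PoCE component (5.1), 7.12 accepts civil-registry notification, and 8.5 times events by the date on which they took place. Only the handling of the unobserved interval before such a death is unstated.

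**Reproducing the plan's sample size**

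Inputs from 8.2: p0 = 0.230, p1 = 0.167, one-sided alpha 5%, power 80%.

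N = [(1.645 × √(0.23 × 0.77) + 0.842 × √(0.167 × 0.833)) / 0.063]² = 255.04, rounded up to 256, as stated. Enrolling 260 leaves 4 patients, 4/260 = 1.5%, for attrition.

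**Pass rule at n = 260 with complete follow-up**

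Upper limit = k/260 + 1.645 × √(p(1−p)/260), with p = k/260.

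- k = 49: 18.85% + 1.645 × 2.425% = 22.84%, pass.
- k = 50: 19.23% + 1.645 × 2.444% = 23.25%, fail.

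At a true PoCE of 23%, P(Bin(260, 0.23) ≤ 49) = 6.2%. The excess over 5% comes from the normal-approximation limit, not from the censoring question.

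**Effect of the adverse reading**

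Assumptions, none of them in the protocol: 4 of the 23 points are deaths, so 19 are non-fatal; a share s of 25% to 50% of these patients' non-fatal events falls after last contact. Let m be the share of patients known only by vital status. The measured rate is then p = 0.23 − 0.19 × m × s, missed events are 260 × 0.19 × m × s, and false success is P(Bin(260, p) ≤ 49).

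| m | Missed events | Measured PoCE | False success |
|---|---|---|---|
| 4/260 (1.5%) | 0.19–0.38 | 22.93–22.85% | 6.6–6.9% |
| 5% | 0.62–1.24 | 22.76–22.53% | 7.4–8.7% |
| 10% | 1.24–2.47 | 22.53–22.05% | 8.7–12.0% |

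Only the first row uses an attrition figure from the protocol, and it supposes that all four patients are known by vital status alone.

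**Kaplan-Meier check**

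A simulation under the same event mix used last contact at day 30 or 180, half of the non-fatal events by day 30, and 20,000 trials per setting. At a 5% share, false success was 7.5–8.5% with carry-forward and 5.8–6.1% with censoring at last contact; in the latter case mean PoCE was 23.0%, so the natural reading is unbiased when loss is non-informative. A separate simulation of this model at the 1.5% share (10,000 trials per setting) found that the two readings gave different decisions in 0.4–1.0% of trials at a true 23%, and in 0.8–2.4% at the expected 16.7%.

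**The case for a change.** The strongest case for acting has three parts.

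First, the anchor at last contact in 7.12 governs patients classed as lost, and a later sentence of the same section removes that class once vital status is known. Read strictly, no sentence fixes the date for a vital-status-only patient. That stands as a point of drafting. It does not make carry-forward the natural reading, because 8.6 rests on complete event reporting whatever label the patient holds.

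Second, the rule can reverse a verdict on identical data. Take 49 observed events, 20 of them by day 30, and four vital-status-only patients last seen at day 30. Carry-forward gives an upper limit of 22.84% and passes. Censoring at day 30 leaves 260 − 20 − 4 = 236 at risk, so the estimate is 1 − (240/260) × (207/236) = 19.04%; with the Greenwood standard error of 2.448% the upper limit is 23.06%, which fails. The arithmetic is right, but the example sits on the last passing count. The binomial chance of exactly 49 events is 1.7% at a true 23% and 4.2% at 16.7%.

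Third, the effect grows with the share. With 30% of non-fatal events early, last contact at day 30 and a 5% share, carry-forward gives 9.8% false success. In another simulation (40% of events in the first 30 days, 20% of events fatal) a 15% share gave about 18%. These figures hold under their assumptions, but a 5% to 15% share is about 3 to 10 times the planned attrition. The three documented attempts per visit in 7.11 and the in-hospital ECG, biomarkers and event recording in 7.8 work against so large a share and against missing early events.

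The further safeguards that might be asked for add little. Counting registry deaths while censoring survivors at last contact, if made an explicit primary rule, raises mean PoCE by 0.1 to 0.2 points at a 5% share and lowers power there to 81.6–82.2%, against 82.8–83.1% with plain censoring at last contact. A tipping-point table for about four patients is a matter of preference.

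**Conclusion.** The concern does not call for a change. Section 8.6 leaves a detail unwritten, but its own condition of complete event reporting leads an analyst to censor a vital-status-only patient at the last contact where events were ascertained. A registry death already enters PoCE through all-cause mortality, at its date.

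Even the adverse reading costs little at the planned attrition: 0.2 to 0.4 missed events, and false success of 6.6–6.9% against 6.2% at a true PoCE of 23%. This rests on all 4 of 260 being vital-status-only, 4 of the 23 points being deaths, and 25% to 50% of those patients' non-fatal events falling after last contact.

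A clause saying that an alive result does not extend event-free time would be harmless, but a sound primary analysis does not depend on it. The conclusion would weaken if the vital-status-only share reached 5% or more, which the protocol gives no reason to expect.
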